## **2.8 PD and PK/PD analyses**

This analysis will be reported separately.

## **2.9 Immunogenicity**

All immunogenicity results will be listed by treatment group, subject and visit/time.

## **2.10 Resource utilization**

Data relating to resource utilization will be used for the purpose of economic evaluation and will be carried out and reported as a separate activity.

## 2.11 Patient-reported outcomes

These analyses will use the FAS.

### Dermatology Life Quality Index (DLQI)

The Dermatology Life Quality Index (DLQI) is a 10-item dermatology-specific HRQoL measure presented to each subject from the randomization to the study end. The instrument contains six subscales (i.e. symptoms and feeling, daily activities, leisure, work and school, personal relationships, treatment). For the DLQI, each of the 10 items is answered with the following response: “not at all,” “a little,” “a lot,” or “very much”. “not relevant” is also a valid response. Seven scores will be derived from the DLQI: the total score of each of the six subscales as well as the total score over all items. The higher the score, the more quality of life is impaired. The DLQI total score will be calculated by summing the score of each item resulting in a maximum of 30 and a minimum of 0. For details of DLQI scoring and interpretation please refer to [Section 5.5.1](#).

Handling of missing values:

- Step 1: if there is only one item with missing score at a visit, it will be imputed as 0 and the subscale including this item and also the total score will be calculated accordingly.
- Step 2: If there are two or more items with missing scores at a visit, the scores for these two items will be missing, so is the subscale including this item and also the total score.

Summary statistics will be provided for absolute and percentage change from baseline of each of the six subscales as well as the total score by visit up to Week 52.

The DLQI scores as well as DLQI responders will be plotted over time. The median will be displayed for the DLQI score per visit and group. For DLQI responders, the rate will be calculated per visit and group and displayed as bar charts.

### Work Productivity and Activity Impairment Questionnaire: Specific Health Problem (WPAI-SHP)

The WPAI-SHP has four subscales, which include Absenteeism, Presenteeism, Work Productivity Loss, and Activity Impairment.

The scores for these subscales are expressed as impairment percentages.

Questions:

- 1 = currently employed
- 2 = hours missed due to specified problem
- 3 = hours missed other reasons
- 4 = hours actually worked
- 5 = degree problem affected productivity while working
- 6 = degree problem affected regular activities

Scores: (Each of the below scores is multiplied by 100 to be expressed in percentages.)

- Absenteeism is the percent work time missed due to problem:  $Q2/(Q2+Q4)$
- Presenteeism is the percent impairment while working due to problem:  $Q5/10$

- Work Productivity Loss is the percent overall work impairment due to problem (absenteeism and presenteeism):  $Q2/(Q2+Q4)+[(1-(Q2/(Q2+Q4)))x(Q5/10)]$
- Activity Impairment is the percent activity impairment due to problem:  $Q6/10$

Absolute change from baseline of WPAI component scores and the absolute WPAI component score will be provided by visit up to end of study.

[figure not shown]
### **EQ-5D-3L**

The EQ-5D-3L is a questionnaire with 5 questions (regarding mobility, self-care, usual activities, pain/discomfort, and anxiety/depression) each with three categories (no problem, moderate problem, severe problems) and a health state assessment from 0 (worst possible health state) to 100 (best possible health state). The number and percentage of subjects in each of the three categories for each question will be presented by visit up to Week 52 for each treatment group. Summary statistics will be shown for absolute and percentage change from baseline of the health state assessment (VAS score) by visit up to Week 52 for each treatment group.

### **PGI (PGI-s and PGI-c)**

Summary statistics will be shown for absolute and percentage change from baseline of PGI-s and PGI-c by visit up to Week 52 for each treatment group.

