
 To evaluate the safety and tolerability of secukinumab over 52 weeks of treatment. To explore the long-term effect of secukinumab with respect to HiSCR, AN count, proportion of patients with flares, HS related skin pain up to 52 weeks of treatment. To evaluate the effect of secukinumab with respect to the following efficacy assessments: 
 Modified Hidradenitis Suppurativa Score (mHSS); HS-Physician's Global Assessment (HS-PGA); 
 Dermatology Life Quality Index (DLQI); Health Status Questionnaire (EQ-5D-3L); Patient Global Impression of severity (PGI-s); Patient Global Impression of change (PGI-c); Work Productivity and Activity Impairment (WPAI); HS Symptom Diary; Inflammatory markers with respect to CRP and ESR compared to placebo after 16 weeks and in the two secukinumab dose regimens up to 52 weeks of treatment. To evaluate the pharmacokinetics of secukinumab in HS patients. To assess the development of immunogenicity against secukinumab. To explore the potential association of biomarker levels with secukinumab efficacy and safety by visit up to Week 52 visit (EOT2). 	
 Clinical safety and tolerability assessments: 
 physical exams, vital signs, laboratory assessments, AE monitoring Achievement of clinical response as defined by HiSCR. Absolute and percentage change from baseline in AN count. Flares Achievement of pain relief as defined by NRS30. Absolute and percent change from baseline in modified Hidradenitis Suppurativa Score (mHSS). HS-PGA response. HS-PGA response is defined as the achievement of at least a 2-point reduction in HS-PGA score compared to baseline. DLQI response and absolute/percent DLQI total score change from baseline. DLQI response is defined as a decrease greater than 5.0 points from baseline. EQ-5D-3L Categories on Category questions and summary statistics on EQ -5D -3L score questions. Patient Global Impression of severity and change (PGI-s and PGI-c) categories. Absolute and percent change from baseline in Work Productivity and Activity Impairment - Specific Health Problem (WPAI-SHP). HS Symptom Diary items score change from baseline. Absolute and percent change from baseline in CRP and ESR 
 AIN457 levels in serum anti-AIN457 antibodies levels in serum Biomarkers in serum

Objective(s)	Endpoint(s)

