8.3.9 Patient Global Impression of Change (PGI-c)

The Patient Global Impression of change (PGI-c) is a patient-reported instrument that measures change in overall status on a scale ranging from one ("very much improved") to seven ("very much worse"). PGI-c rates the current HS symptoms as compared to the start of the study at visits indicated in the assessment schedule. The PGI-c is self-administered and is to be completed as per the assessment schedule on the electronic tablet at the investigational site. The PGI-c is based on the validated Clinical Global Impression of change scale.

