- To allow for a pairwise comparison between two secukinumab regimens and placebo until Week 16, DLQI score up to Week 16 will also be analyzed using a MMRM with treatment group, the respective baseline value, Hurley stage, use of antibiotic, geographical region, baseline bodyweight, visit, baseline DLQI*visit interaction, and treatment group*visit as covariates, with unstructured covariance matrix.

Work Productivity and Activity Impairment (WPAI)

Summary statistics will be provided for absolute and percentage change from baseline of WPAI component scores by visit up to end of study.

EQ-5D-3L

The EQ-5D is a questionnaire with 5 questions (regarding mobility, self-care, usual activities, pain/discomfort, and anxiety/depression) each with three categories (no problem, moderate problem, severe problems) and a health state assessment from 0 (worst possible health state) to 100 (best possible health state). The number and percentage of subjects in each of the three categories for each question will be presented by visit up to the end of study for each treatment group. Summary statistics will be shown for the health state assessment by visit up to the end of study for each treatment group.

PGI (PGI-s and PGI-c)

The number and percentage of subjects in each category will be presented by visit up to the end of study for each treatment group.

HS Symptom Diary

Summary statistics will be provided for absolute and percentage change from baseline of HS symptom component scores and the absolute HS symptom component score by visit up to end of study.

Inflammatory markers with respect to CRP and ESR

Summary statistics will be provided for absolute and percentage change from baseline of CRP and ESR by visit up to end of study.

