## 1 Introduction

The purpose of this Statistical Analysis Plan (SAP) is to describe the implementation of the statistical analysis for the following study:

CAIN457M2302 - A randomized, double-blind, multicenter study assessing short (16 weeks) and long-term efficacy (up to 1 year), safety, and tolerability of 2 subcutaneous secukinumab dose regimens in adult patients with moderate to severe hidradenitis suppurativa (SUNSHINE).

Data will be analyzed by Novartis according to the data analysis Section 12 of the study protocol which is available in Appendix 16.1.1 of the CSR. Important information is given in the following sections and details are provided, as applicable, in Appendix 16.1.9 of the CSR.

This document covers statistical and analytical plans for the final Week 52 analysis after all subjects have completed the study.

All analysis related to the primary and secondary objectives in the testing hierarchy are described in the Week 16 Primary Endpoint Analysis (PEA) SAP and are not covered in this final Week 52 SAP. The study and list of primary, secondary and exploratory objectives are kept for background.

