## **2 Statistical methods**

### **2.1 Data analysis general information**

Novartis will be performing the analysis. Statistical software SAS version 9.4 or later will be used.

Summary statistics for continuous variables will include N, mean, standard deviation, minimum, lower quartile, median, upper quartile, maximum. Summary statistics for discrete variables will be presented in contingency tables and will include absolute and relative frequencies. Unless otherwise stated, summary tables/figures/listings will be based on all subjects included in the population under consideration.

Listings will be presented by treatment arms.

Footnotes will generally be provided for:

- abbreviations used in the output; abbreviations used on several outputs, e.g. for listings in Appendix 16.2 can be presented on a separate page and do not have to be repeated as footnotes on each listing
- sorting order of categories, e.g. for sorting within MedDRA (Medical Dictionary for Regulatory Activities) hierarchy levels
- MedDRA version used for reporting of MedDRA coded data

Footnotes will generally NOT be given for

- units displayed on the output

- interpretation of results (e.g., “odds ratio larger 1 favors active treatment”)
- information that can be retrieved from the statistical section of the clinical study report (CSR) unless it is not identifiable from the output, e.g.
  - explanation of analysis model used unless results of more than one model are displayed in an output
  - derivations of variables (e.g. BMI will not be explained in a footnote)
- information that will be provided in the clinical study protocol and/or methods section of the CSR (e.g. baseline definition if this is specified in the statistical section of the CSR)

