## 4 Change to protocol specified analyses

Response of HS-PGA is defined as the achievement of at least a 2-point reduction in HS-PGA score compared to baseline or the achievement of a “mild” status (defined as achieving an HS-PGA score of  $\leq 2$ ). While in the Protocol it is defined as at least a 2-point reduction in HS-PGA score only.

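### SAP 2.11 summarises PGI-c, itself a rating of change since study start, as change from baseline; the SAP also gives two rules for a two-item DLQI subscale with one missing item

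*SAP*

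**What the plan says.** **PGI.** The PGI paragraph of SAP 2.11 reads: "Summary statistics will be shown for absolute and percentage change from baseline of PGI-s and PGI-c by visit up to Week 52". It names no other PGI output. Protocol 8.3.9 describes PGI-c as a self-rating from 1 (best) to 7 (worst), and adds: "PGI-c rates the current HS symptoms as compared to the start of the study". Protocol Table 2-1 gives the endpoint as "Patient Global Impression of severity and change (PGI-s and PGI-c) categories", and SAP Table 1-1 repeats it. The PGI paragraph of protocol 12.6 specifies: "The number and percentage of subjects in each category will be presented by visit up to the end of study for each treatment group".

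SAP Section 4, which records changes from the protocol analyses, has one entry. It concerns the HS-PGA response definition and ends: "While in the Protocol it is defined as at least a 2-point reduction in HS-PGA score only".

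**DLQI, missing item.** Under SAP 2.11 (Step 1), a single missing item is set to 0, and both its subscale and the total are calculated. Under SAP 5.5.1 (rule 6), a two-item subscale with one item missing is not scored.

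**DLQI response.** Protocol Table 2-1 and SAP Table 1-1 require a decrease of more than 5.0 points; protocol 12.6 requires a decrease of at least 5.0. SAP 2.11 plans responder bar charts by visit and does not repeat a cut-off.

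**The concern.** The comparison with study start is built into the PGI-c item. Subtracting a start value from it, or dividing by one, applies the comparison twice. A percentage change of such a rating could also be misread as a percentage improvement in the disease. Followed literally, SAP 2.11 puts that table in the study report, with no Section 4 entry to explain why it is there when three other places specify categories.

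The DLQI subscale rules cannot both be programmed. SAP 2.11 plans change-from-baseline summaries for all six subscales, so the conflict reaches a planned output.

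**Working it through.** The plan gives no figure to reproduce here. The check compares the texts and uses simple arithmetic to show what each rule does.

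**1. PGI-c.** Inputs: the 1 to 7 scale (protocol 8.3.9) and the change-from-baseline instruction (SAP 2.11). Let r be the rating at a visit and b the rating at baseline. Absolute change = r − b; percentage change = 100 × (r − b)/b. The documents give no baseline ratings, so b is assumed.

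*Assumption A: every patient enters the midpoint, b = 4.*

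| r | r − 4 | % change |
|---|---|---|
| 1 | −3 | −75 |
| 2 | −2 | −50 |
| 3 | −1 | −25 |
| 4 | 0 | 0 |
| 5 | +1 | +25 |
| 6 | +2 | +50 |
| 7 | +3 | +75 |

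This only relabels the seven categories.

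*Assumption B: b varies from 3 to 5.* The same Week 52 rating, r = 2, gives:
- b = 3: −1, or 100 × (−1)/3 = −33.3%
- b = 4: −2, or 100 × (−2)/4 = −50.0%
- b = 5: −3, or 100 × (−3)/5 = −60.0%

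Three patients report the same change since study start and receive three different values. The spread comes from a start rating that has no earlier time point to refer to.

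**2. Comparison within SAP 2.11.** The EQ-5D-3L paragraph just before the PGI paragraph says: "The number and percentage of subjects in each of the three categories for each question will be presented by visit up to Week 52". It keeps change from baseline for the VAS score. The PGI paragraph makes no such split between categorical and numerical parts.

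**3. DLQI subscale.** SAP 5.5.1 lists four two-item subscales (questions 1–2, 3–4, 5–6 and 8–9) and two single-item ones (7 and 10). The conflict therefore covers 4 of 6 subscales and 8 of 10 items. Example: baseline 2 + 2 = 4; at Week 52 one item is 2 and the other is missing.
- SAP 2.11, Step 1: score 2 + 0 = 2; change (2 − 4)/4 = −50%.
- SAP 5.5.1, rule 6: no score and no change.

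The total is unaffected. Both sections score a single missing item as 0 in the total, and both leave the total missing when two or more items are missing.

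**4. DLQI response.** The definitions differ only for a drop of exactly 5: a drop of 4 is a non-response and a drop of 6 a response under both. To illustrate size, take change as a normal variable with mean m and SD s, rounded to an integer:

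P(change = −5) = Φ((−4.5 − m)/s) − Φ((−5.5 − m)/s)

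With m from −1 to −6 and s from 5 to 8 (all assumed), the smallest value is 0.0440 (m = −1, s = 8) and the largest is 0.0797 (m = −5, s = 5). One responder rate would then differ by 4.4 to 8.0 percentage points between the definitions. This is illustration only: the DLQI is bounded at 0 and 30, and a patient who starts below 5 cannot fall by 5.

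**The case against.** The strongest reply is that the category counts are not lost. SAP Section 1 says that data will be analysed "according to the data analysis Section 12 of the study protocol". SAP 2.1 says: "Summary statistics for discrete variables will be presented in contingency tables and will include absolute and relative frequencies", and SAP 5.4.2.1 repeats this. SAP Table 2-7 lists PGI simply as descriptive. On this reading the PGI paragraph adds a summary and removes nothing, and whether Section 4 must list an added descriptive table is open to debate. This stands as far as it goes: a reader might infer that the SAP has dropped the categories, and the documents do not support that. But general text does not cancel a specific instruction to tabulate PGI-c change.

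Four other tempting inferences also fail.
- *PGI-s change is equally meaningless.* It is not. PGI-s rates current severity, so a change in it can be interpreted. It is only unlisted in Section 4.
- *Table 8-1 settles whether PGI-c has a baseline value.* The column alignment in the text copy used here is unreliable: read literally, it starts DLQI, EQ-5D and HS-PGA at Week 1, although DLQI and HS-PGA responses are defined against baseline. Nothing here rests on that table.
- *The SAP leaves the DLQI cut-off open.* SAP Table 1-1 fixes it at more than 5.0, in agreement with protocol Table 2-1. The inconsistency starts inside the protocol, between Table 2-1 and 12.6.
- *The cut-off could distort a Week 52 comparison with placebo.* No such comparison exists. All patients receive secukinumab from Week 16 (protocol Section 3), and the efficacy groups in SAP 2.3.1 are two secukinumab arms and two arms that switched from placebo.

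Missing DLQI items are also likely to be few, because protocol 8.5.1 has the coordinator check questionnaires for completeness.

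**Conclusion.** The PGI-c summary in SAP 2.11 is wrong as written: at best it restates the rating minus a constant, and otherwise it mixes in a start rating that carries no information about change. That conclusion rests on the item definition in protocol 8.3.9; the numerical examples depend on assumed baseline ratings. The Week 16 primary endpoint SAP, which is not among the documents, could not remove the conflict: protocol 12.6 asks for categories up to the end of study, and this SAP governs the final Week 52 analysis.

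The contradiction over two-item DLQI subscales is real. It affects four of six subscales at an unknown and probably low frequency. The cut-off difference amounts to a missing cross-reference.

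Severity is minor. Every affected outcome is exploratory, descriptive in this SAP and outside the testing strategy. No primary or secondary result, alpha level or power figure changes.

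**What to change.** 1. In SAP 2.11, report PGI-s and PGI-c as counts and percentages per category at each visit, and drop change from baseline for PGI-c. A PGI-s change summary may stay if it is listed in SAP Section 4.
2. State one rule, either of the two, for a two-item DLQI subscale with one missing item, and use it in both SAP 2.11 and 5.5.1. Leave the total-score rule as it is.
3. Add a Section 4 entry saying that the Week 52 DLQI responder charts use the SAP Table 1-1 cut-off (more than 5.0), which differs from protocol 12.6 (at least 5.0).

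The cost is wording in three SAP sections, with at most two new Section 4 entries, and revised PGI table shells. Depending on the DLQI rule chosen, a few subscale scores become missing or include an item set to 0. No new data and no protocol amendment are needed; the protocol's own two cut-offs remain, but the Section 4 entry makes clear which one was used.

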### **HS Symptom Diary**

For analysis of HS Symptom Diary, the weekly average HS Symptom component score from baseline to Week 52 is calculated based on the 7 available daily scores: Baseline (Week 0) will be average of HS symptom Diary score from day -7 to day -1, Week 1 will be average of score from day 1 to day 7, Week 2 will be average of score from day 8 to day 14 and so on. For any week with less than 4 diary entries within the week, the weekly average component score will be recorded as missing. HS symptom Diary questions will be collected at specific visits only after Week 16 per pre-defined assessment schedule, thus HS Symptom component score after Week 16 is not provided as a weekly average but as single values. Statistics will be provided for absolute and percentage change from baseline of HS symptom component scores by visit up to Week 52 for each treatment group.

### **Additional endpoints**

Patient's Global Assessment of Skin Pain - at worst will be summarised on the original scale.

The analysis results on Patient assessed lesion count will be reported separately.

## 2.12 Biomarkers

All biomarker data will be listed by treatment group, subject and visit. Summary statistics will be provided by treatment and visit.

## 2.13 Other Exploratory analyses

[Table 2-7](#) lists the primary, secondary and exploratory variables for this study. Unless otherwise specified in related sections, observed data will be used up to Week 52.

**Table 2-7 Exploratory variables**

Variable	Type	Model	Missing data handling
HiSCR over time	exploratory	MELRM descriptive	use observed data only
Flare over time	exploratory	MELRM Kaplan Meier descriptive	use observed data only
AN count over time	exploratory	MMRM descriptive	use observed data only
AN50 over time	exploratory	MELRM descriptive	use observed data only
NRS30 over time	exploratory	MELRM descriptive	use observed data only
HiSCR25, HiSCR75, HiSCR90, HiSCR100 over time	exploratory	descriptive	use observed data only
AN25, AN50, AN75, AN90, AN100 AN 0/1, AN0/1/2 over time	exploratory	descriptive	use observed data only
No increase in draining fistulæ over time	exploratory	descriptive	use observed data only
No increase in abcesses over time	exploratory	descriptive	use observed data only
Inflammatory nodules, abcesses, draining fistulæ change from baseline over time	exploratory	descriptive	use observed data only
DLQI total score and component score over time	exploratory	descriptive	use observed data only
WPAI-HS over time	exploratory	descriptive	use observed data only
HS-dairy over time	exploratory	descriptive	use observed data only
PGI-s and PGI-c over time	exploratory	descriptive	use observed data only
EQ-5D	exploratory	descriptive	use observed data only

Following analyses will use the FAS.

### **Hidradenitis Suppurativa Clinical Response (HiSCR) components and alternative definitions**

The number and percentage of HiSCR subjects will be presented by visit up to Week 52 for each treatment group, where HiSCR is defined as at least a 50% decrease in Abscess and Inflammatory Nodule (AN) count with no increase in the number of abcesses and/or in the

number of draining fistulae compared to baseline. Observed values will be presented for data up to Week 52.

Figures will be provided displaying estimates for responder rates by treatment groups including confidence intervals. The below lesion information will be presented by visit up to Week /52 for each treatment group. The number and percentage will be presented for subjects who achieved at least 25%, 50%, 75%, 90% and 100% reductions in the AN count relative to Baseline (AN25, AN50, AN75, AN90, AN100). Furthermore, the number and percentage will be presented for subjects who showed an AN count of either 0 or 1 (AN0/1) and for subjects who showed an AN count of either 0 or 1 or 2 (AN0/1/2).

- The number and percentage will be presented for subjects with no increase in the number of abscesses. Furthermore, the number and percentage of subjects with no increase in draining fistulae will be presented.
- Analogously, the number and percentage will be presented for subjects who achieved a slight modification of the HiSCR response: at least 25%, 75%, 90% and 100% reductions in the AN count with no increase in the number of abscesses and/or in the number of draining fistulae relative to baseline (HiSCR25, HiSCR75, HiSCR90, HiSCR100).
- Summary statistics will be presented for absolute and percent change from baseline for number of inflammatory nodules/abscesses/AN counts/draining fistulae. The following visualizations will be provided: The number of inflammatory nodules/abscesses/AN counts/draining fistulae will be plotted over time. For this, the mean will be provided per visit and group. Furthermore, the relative change from baseline in AN counts to Week 52 will be displayed per group using violin plots. Similarly, the absolute change from baseline in number of abscesses and draining fistulae to Week 52 will be displayed per group using violin plots.
- A mixed effects logistic regression model (MELRM) will be fitted. The endpoint is HiSCR at all time points from Week 2 up to Week 52 and are included on the left hand side of the model as dependent variables. The covariates included as fixed effects are: treatment group, visit, baseline AN count and the interaction between visit and treatment group. An unstructured covariance structure will be applied. In case of non-convergence, alternative covariance structures will be considered. If additional convergence issues are encountered, then modifications to the model will be considered.

